4. SUBJECT SELECTION

4.1. Study Population

Subjects must meet all the inclusion criteria and none of the exclusion criteria to be eligible for participation in this study.

4.2. Inclusion Criteria

- 1. Willing and able to provide informed consent.
- 2. Positive SARS-CoV-2 diagnostic test (RT-PCR or validated rapid antigen test) conducted ≤ 5 days prior to randomization. *Note: The test may be obtained locally. A documented historical record of positive result (RT-PCR or validated rapid antigen test) from test conducted* ≤ 5 days prior to randomization is acceptable.
- 3. Mild or moderate COVID-19 with symptom onset ≤ 5 days before randomization and at least one COVID-19 related symptom present at time of screening:
- Mild COVID-19:
 - Symptoms of mild illness with COVID-19, which could include fever, cough, sore throat, malaise, headache, muscle pain, nausea, vomiting, diarrhea, and loss of taste or smell, without shortness of breath or dyspnea
 - No clinical signs indicative of moderate, severe, or critical illness severity
- Moderate COVID-19:
 - Symptoms of moderate illness with COVID-19, which could include any symptom of mild illness or shortness of breath with exertion
 - Clinical signs suggestive of moderate illness with COVID-19, such as respiratory rate ≥ 20 breaths per minute, heart rate ≥ 90 beats per minute; with saturation of oxygen (SpO2) > 93% on room air
 - No clinical signs indicative of severe or critical illness severity
- 4. For females of childbearing potential: agreement to remain abstinent (refrain from heterosexual intercourse) or use adequate contraception during the treatment period and for 30 days after the final dose of study drug.
- 5. Females of childbearing potential must have a negative pregnancy test prior to initiation of study drug.
- 6. Subject must be able to take oral tablet medications.
- 7. Subject is, in the opinion of the investigator, willing and able to comply with the study drug regimen and all other study requirements.
- 8. Subject must be high risk, defined below.
- Age \geq 70 years OR
- Age \geq 55 years with one of the following risk factors:

- Obesity (body mass index [BMI] \ge 30 kg/m²)
- Diabetes mellitus
- Cardiovascular disease (including congenital heart disease) or hypertension (with at least one medication recommended or prescribed)
- Chronic lung disease requiring routine therapy (eg, chronic obstructive pulmonary disease [COPD], moderate-to-severe asthma, interstitial lung disease, cystic fibrosis, pulmonary hypertension)

OR

- Age 50 to 54 inclusive with two of the following risk factors:
 - Obesity (body mass index [BMI] ≥30 kg/m²)
 - Diabetes mellitus
 - Cardiovascular disease (including congenital heart disease) or hypertension (with at least one medication recommended or prescribed)
 - Chronic lung disease requiring routine therapy (eg, chronic obstructive pulmonary disease [COPD], moderate-to-severe asthma, interstitial lung disease, cystic fibrosis, pulmonary hypertension)

OR

- Age \geq 18 years with one of the following:
 - Down syndrome
 - Sickle cell disease
 - Dementia
 - Parkinson's disease
 - Care home residents
 - One of the following immunocompromising conditions or immunosuppressive treatments:
 - On immunosuppressive regimens including chemotherapy for the treatment of cancer
 - Hematologic malignancy associated with poor response to COVID-19 vaccines (eg, CLL, non-Hodgkin lymphoma, multiple myeloma, acute leukemia)
 - o Being within 2 years of a hematopoietic stem cell transplant
 - o Receipt of a solid-organ transplant and on immunosuppressive therapy
 - Human immunodeficiency virus (HIV) infection (untreated) or with CD4⁺ T lymphocyte count <350 cells per cubic millimeter (mm³)
 - o Moderate or severe primary immunodeficiency disorder

- O Active treatment with an immunosuppressive medication regimen (eg, high-dose corticosteroids [ie, 20 mg of prednisone daily or equivalent for ≥2 weeks], alkylating agents, antimetabolites, transplant-related immunosuppressive drugs, cancer chemotherapeutic agents that are severely immunosuppressive, anti-tumor necrosis factor (TNF) blockers, biologics that are immunosuppressive)
- Enrollment of 24 high-risk adolescents (≥ 12 years to 17 years) will be allowed after the planned interim analysis for which 65% of the supportive-care-only stratum completed the follow-up period (Day 29). A DSMB recommendation that the study continue at this interim analysis point will trigger enrollment of adolescents. The Sponsor will notify sites when enrollment of adolescent subjects is permitted. *Note: "High-risk" subjects in this age group are identical to high-risk subjects* ≥ 18 years.

4.3. Exclusion Criteria

- 1. Female subject is pregnant or breastfeeding.
- 2. Clinical signs or symptoms indicative of severe or critical COVID-19 illness, including any of the following: shortness of breath at rest, respiratory rate ≥ 30 breaths per minute, heart rate ≥ 125 beats per minute, SpO2 ≤ 93% on room air , partial pressure of oxygen/fraction of inspired oxygen (PaO2/FiO2) <300, shock (defined by systolic blood pressure < 90 mm Hg or diastolic blood pressure < 60 mm Hg or requiring vasopressors), multi-organ dysfunction/failure, respiratory distress, respiratory failure; requirement of endotracheal intubation, mechanical ventilation, oxygen delivered by high-flow nasal cannula, noninvasive positive pressure ventilation, extracorporeal membrane oxygenation (ECMO).

Note: Subjects receiving chronic supplemental oxygen by nasal cannula are eligible for the study if there has been no increase in baseline oxygen requirement/settings.

- 3. Admitted to a hospital within 90 days prior to randomization due to COVID-19 or is hospitalized (inpatient) for any reason at randomization.
 - Note: If local policy requires COVID-19 isolation or internment in a hospital or similar facility, but subjects otherwise meet criteria, this exclusion may not apply. However, subjects under clinical observation at a clinic/study site or hospital with plans to remain in that setting overnight are not study eligible.
- 4. In the opinion of the investigator, is likely to experience imminent deterioration and require hospitalization within 24 hours.
- 5. Use of other investigational drugs within 30 days prior to planned dosing, or plans to enroll in another clinical trial of an investigational agent while participating in the present study, except for unblinded protocols that don't include direct acting antivirals for COVID-19 (eg, open-label oncological regimen variations or biologic studies). Note: Prior to enrolling subjects that are on other open-label studies, it is the site's responsibility to ensure that the study criteria for that study allow for enrollment into this study.

- 6. Initiation or planned initiation of remdesivir for treatment of the current SARS-CoV-2 infection.
- 7. Requirement of any prohibited medications, as described in Section 5.7, including either hydroxychloroquine or amiodarone within 3 months prior to screening. (see rationale in Section 5.7.5)
 - Note: Subjects who had already initiated any COVID-19 drug with antiviral effects intended to treat symptomatic SARS-CoV-2 infection (≥ 24 hours prior to randomization) will be excluded. During screening (or within 24 hours prior to or after randomization), locally available COVID-19 drugs with antiviral effects (including but not limited to nirmatrelvir/ritonavir, molnupiravir, favipiravir, mAbs) will be permitted, as long as there are no concerns for DDIs (eg, remdesivir would not be permitted).
- 8. Other known active viral or bacterial infection at the time of screening, such as influenza (ie, as verified by a locally available rapid flu test at screening) or respiratory syncytial virus (RSV).
 - Note: This exclusion does not apply to subjects with stable chronic viral infections, such as chronic HCV or HIV providing other eligibility criteria are met.
- 9. Receiving dialysis or have severe renal impairment [ie estimated glomerular filtration rate (eGFR) <30 mL/min/1.73 m2 within 6 months of the screening visit, using the serum creatinine-based CKD-EPI formula]. Note: If the investigator suspects the subject may have eGFR <30 mL/min/1.73 m², a confirmatory test should be performed at screening to confirm eligibility before the first dose of study drug.
- 10. History of severe hepatic impairment (Child-Pugh Class C)
- 11. Known allergy or hypersensitivity to components of study drug.
- 12. Malabsorption syndrome or other condition that would interfere with enteral absorption.
- 13. Any clinically significant medical condition or known laboratory abnormality that, in the opinion of the investigator, could jeopardize the safety of the subject or impact subject compliance or safety/efficacy observations in the study.

One-time retests of individual screening laboratory parameters or assessments may be permitted in certain scenarios. Such scenarios may include lab processing error, results inconsistent with subject's historical values/medical history, or other extenuating circumstances such as a recent or intercurrent illness potentially affecting screening laboratory results.

5. STUDY TREATMENTS

5.1. Description and Handling of Study Treatments

5.1.1. Test Product

BEM will be provided by the Sponsor as 275 mg tablets (designated as formulation A2-275 mg).

5.1.2. Control Product

Matching placebo tablets for BEM will be provided by the Sponsor.

5.1.3. Packaging and Labeling

The Sponsor will be responsible for ensuring that study drugs (active and placebo) are manufactured in accordance with applicable Good Manufacturing Practice regulations and requirements. The labels for the study drug(s) will meet applicable local regulatory requirements.

5.1.4. Storage and Handling

Study drugs should be stored under the conditions described on the label.

5.1.5. Background Standard of Care

Study drug (BEM or placebo) should be administered as an "add-on" therapy to locally available SOC. Depending on the region, SOC may either include compatible antiviral treatments (such as nirmatrelvir/ritonavir, molnupiravir, favipiravir, mAbs or other COVID-19 drugs with antiviral effects) or alternatively be deemed 'supportive care only' (and not include treatment with COVID-19 drugs with antiviral effects). Standard of care is administered at the discretion of the investigator, based on local practice, and includes therapies or treatments that are locally available to the investigator/site. SOC is not a study drug and is therefore not provided by the Sponsor. However, the type of background SOC that is administered must be documented and captured in the electronic case report form (eCRF).

Patients who require SOC treatment with a non-compatible antiviral treatment, defined as those with a potential DDI with BEM (eg, remdesivir), are excluded.

Auxiliary Medicinal Products (for EU sites)

Compatible antiviral treatments as SOC, such as direct acting antivirals and mAbs, are considered auxiliary medicinal products in this study as per EU regulation No 536/2014 Article 2 (8) and should be used in accordance with the terms of their marketing authorization. Nirmatrelvir/ritonavir is an example of an authorized auxiliary medicinal product. Some compatible antiviral treatments utilized as SOC in the combination antiviral arm of this trial outside of the EU may not be available in the EU; all antivirals will be administered in accordance with their approved local usage.

5.2. Method of Assigning Subjects to Treatment Groups

A unique subject number will be assigned to each subject at screening. Once assigned, it will not be reassigned to another subject. Once eligibility is confirmed, subjects will then be randomly assigned to a treatment group (active vs. placebo) according to a randomization list, generated by the designated independent biostatistician. This will be through a centralized randomization process and eligible subjects may also receive a unique randomization number linked to a treatment assignment. Randomization will be stratified by geographic region (North America, Europe, Asia, and ROW), age (< 65 years old vs ≥ 65 years old) and by the type of SOC which the investigator plans to administer in parallel at time of study drug initiation (combination antiviral vs supportive-care-only). The primary stratification factor is the type of background SOC that the investigator plans to administer as this determines whether the subject is in the supportive-care only group (ie may be included in the primary analysis population) or the combination antiviral group. Within each of the primary strata, randomization is further stratified by geographic region (North America, Europe, Asia, and ROW) and age (< 65 and ≥ 65).

5.3. Blinding

Study site personnel and subjects will be blinded to treatment assignment during the study. The Sponsor and its agents will also be blinded to treatment assignment, with the exception of individuals who require access to treatment assignments to fulfill their job roles during a clinical trial. These roles include clinical supply chain managers, any laboratory responsible for performing study drug PK, IxRS service provider, and Data Safety Monitoring Board (DSMB) members.

Unless efficacy is demonstrated at an interim analysis, the study blind will not be broken until after all subjects complete the primary study period (through Day 29).

During the study, the blind may be broken for an individual subject by the investigator only in emergencies or when knowledge of a subject's treatment group is necessary for further subject management. Although not necessary in the case of an emergency, the investigator should discuss the specific case with the Sponsor prior to unblinding. The date and reason for breaking the blind must be recorded.

5.4. Dosing and Administration

5.4.1. Dispensing

Designated site staff will dispense the blinded study drugs (active or placebo) to each subject at the Day 1 visit.

5.4.2. Administration Instructions

Study drug dosing should occur on the same day as randomization. Subjects will self-administer BEM 550 mg (2 x 275 mg tablets) or matching placebo (2 tablets) orally BID on Days 1-5. Each dose consists of 2 tablets. On each dosing day, 2 tablets will be taken for the morning dose and 2 tablets will be taken for the evening dose. The total treatment course consists for a total of 10 doses over 5 days (20 tablets total).

BEM (or matching placebo) should be taken orally approximately 12 hours apart, with a minimum of 6 hours apart. If the first study dose is taken prior to 16:00 on Day 1, the next dose should be taken in the evening of the same day (ie prior to midnight on the same calendar day with a minimum of 6 hours between doses). For these subjects, the final (tenth) dose will be taken in the evening of Day 5. However, if the first study dose is taken after 16:00 on Day 1, the next dose should be taken in the morning of Day 2. For these subjects, the final (tenth) dose will be taken on the morning of Day 6.

BEM (or placebo) tablets should be swallowed whole with a glass of water and should not be chewed, cut, crushed, or dissolved.

If a dose of BEM (or placebo) is missed (ie, not taken within 6 hours after the scheduled dosing time), the subject should resume dosing with the next scheduled dose. Subjects should never double the next dose after a missed dose. In this scenario where a dose is missed, the subject should still complete the full course of 10 doses, making up for the missed dose at the end of the dosing period (as opposed to only taking 9 doses). If a subject vomits after taking a dose, a replacement tablet should not be taken, and dosing should resume with the next scheduled dose. Subjects will be instructed to bring their bottles of study drug to each study visit.

BEM can be taken with or without food.

5.4.3. Treatment Compliance

Subjects will be provided with a dosing diary, to record the times at which they self-administer study drug. The dosing diary will be used to assess treatment compliance. Subjects who have difficulty in using the diary (eg, blind, illiterate, physical limitations, unfamiliar with technology) can obtain assistance from close contacts (eg family members or friends) in recording responses but should not obtain advice or help from others with constructing responses.

5.5. Study Drug Accountability

Complete and accurate records of all study drugs must be kept. These include acknowledgment of receipt of each shipment of study product, subject dispensing records, and records of returned or destroyed study product.

At the end of the study, all unused study drugs and containers will be returned to the Sponsor (or designee) or destroyed, per the instruction of the Sponsor. Documentation confirming drug accountability will be reviewed over the course of the trial.

5.6. Premature Treatment or Study Discontinuation

Subjects may voluntarily discontinue treatment or withdraw from the study at any time. They may also be removed from the study at the discretion of the investigator or Sponsor at any time. The investigator may withdraw a subject at any time if it is determined that continuing the study would result in a significant safety risk to the subject.

Premature treatment or study discontinuation may occur for any of the following reasons:

• Persistent noncompliance with the protocol requirements

- **AE**
- Death
- Subject request (withdrawal of consent)
- Investigator request
- Sponsor request
- Loss to follow-up
- Pregnancy

Individual Study Drug Stopping Rules

Study drug treatment will be immediately discontinued in any individual subject who experiences:

- Any treatment-emergent SAE, or AE of grade 3 severity or higher (including confirmed laboratory abnormalities of grade 3 severity or higher reported as AEs) considered by the investigator to be related to study drug
- Confirmed estimated glomerular filtration rate [eGFR] <30 mL/min/1.73 m²
- For subjects with liver function testing within normal limits on the Day 1 lab draw:
 - Confirmed treatment-emergent elevation of alanine aminotransferase (ALT) or aspartate aminotransferase (AST) > 3 x ULN with total bilirubin (TB) > 2 x upper limit of normal (ULN) not due to hemolysis, and without evident alternative cause for these elevations
- For subjects with ALT or AST levels above the upper limit of normal on the Day 1 lab draw:
 - Confirmed treatment-emergent elevation of ALT or AST > 3 x baseline with TB
 2 x ULN not due to hemolysis, and without evident alternative cause for these elevations
- For subjects with TB level above the upper limit of normal on the Day 1 lab draw:
 - Confirmed treatment-emergent elevation of ALT or AST > 3 x ULN with TB >2x baseline level (and not due to hemolysis), and without evident alternative cause for these elevations
- Initiation or planned initiation of remdesivir
- Pregnancy

Hospitalization for the acute management of COVID-19 or other medical conditions does not require discontinuation of study drug; however on-going study drug management will be at the discretion of the PI and treating physicians.

Subjects who prematurely discontinue study drug treatment should be encouraged to remain in the study and maintain the same protocol schedule and assessments as described in Table 1. This will allow for continued subject follow-up for key outcome data. Subjects who prematurely

discontinue the study [prior to Day 29 (primary study period)] and are unable to maintain the same protocol schedule should complete early termination (ET) assessments at the time of study discontinuation, as described in Table 1. Nevertheless, all attempts should be made to contact the subject at Day 29 (telephone contact is acceptable) to confirm key study endpoints, including hospitalization and survival.

The primary study period is through Day 29. The end of the study for any individual subject will be defined as the 60-day follow-up contact.

5.7. Prior Therapy, Concomitant Therapy, Permitted Therapy, Cautionary Therapy, and Prohibited Therapy

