8.3.1. Primary Efficacy Analysis

The primary efficacy objective of this study is to evaluate the efficacy of BEM based on the proportion of patients who are hospitalized for any cause or who died due to any cause through Day 29 in the supportive-care-only population. The primary estimand is the difference in the proportion of patients who are hospitalized for any cause or who died due to any cause through Day 29 in the supportive-care-only population, and the primary treatment effect comparison will be between the BEM arm and the placebo arm. This proportion will be compared between the BEM and placebo arms using a Cochran-Mantel-Haenszel (CMH) test adjusted for the stratification factors of age and region. The CMH p-value and estimated common risk difference, odds ratio and relative risk, along with the corresponding 95% confidence intervals (CIs) for these estimates, will be presented.

Intercurrent events are those that occur after treatment initiation and either preclude observation of the variable or affect its interpretation. For the intercurrent events of rescue (eg intervention with remdesivir) and concomitant COVID-19 medications, a treatment policy approach will be taken, whereby use of rescue and concomitant medications will be ignored and observations collected after they are administered to the patient will be used. In addition, patients will be followed, assessed, and analyzed irrespective of their completion of the course of the study treatment. The analysis will be performed based on observed data, and the following measures will be used to reduce missing hospitalization/death data: eCRFs capturing clinical information that may be indicative of hospitalization will be reviewed to mitigate the risk of unreported hospitalizations, and study staff may use a public information source to obtain information about survival status if a patient withdraws from the study.

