3.2.3. Exploratory Endpoints

Efficacy:

- Time to sustained alleviation or improvement of COVID-19 symptoms
- Time to self-reported return to usual (pre-COVID-19) health
- Proportion of subjects requiring post randomization rescue therapy

Note: For subjects randomized into the combination antiviral population, antiviral medications administered post-baseline within 24 hours of first study drug, as part of the combination regimen, are not considered rescue medication.

Note: Rescue therapy for the purpose of the endpoint includes only treatments with direct activity against SARS-CoV-2; and that is administered for COVID-19-related clinical decline.

- Duration and severity of COVID-19 symptom relapse
- Proportion of subjects with both COVID-19 symptom relapse and viral rebound
- Change from baseline in amount of SARS-CoV-2 viral RNA as measured by RT-qPCR overtime
- Time to cessation of SARS-CoV-2 viral shedding by RT-qPCR
- Proportion of subjects negative for SARS-CoV-2 viral RNA by RT-qPCR over time
- Area under the curve (AUC) in the amount of SARS-CoV-2 viral RNA as measured by RT-qPCR
- Potential future biomarker analyses
- Pharmacokinetics: Plasma concentration of AT-511 (free base form of AT-527 [BEM]) and its metabolites

		Intercurrent	Population- Level Summary	Handling of Missing Data Study Withdrawal/ Lost to Follow-
Estimand Primary: difference in the proportion of subjects in the supportive-care population with all-cause hospitalization or death by Day 29 and Day 60, regardless of intercurrent events	Endpoint The proportion of subjects in the supportive-care-only population who are hospitalized for any cause or died due to any cause through Day 29	event handling Treatment-policy strategy approach will be taken. Patients are followed, assessed and analyzed irrespective of their completion of the planned course of the study treatment and irrespective of rescue and concomitant therapy.	for the Variable The common risk difference	Up The outcome measure up to point of study withdrawal will be used

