8.5. Multiple Comparisons and Multiplicity

If a statistically significant result is found on the test of the primary endpoint, sequential testing will be performed for the secondary endpoints in the following order. When endpoint is tested for both Day 29 and Day 60, the order will be Day 29 first, followed by D60.

- 1. Proportion of subjects in the supportive-care-only population with all-cause hospitalization or all-cause death through Day 60
- 2. Proportion of subjects in the supportive-care-only population with all-cause hospitalization, all-cause death, or COVID-19 related medically attended visits through Day 29 and Day 60.
- 3. Proportion of subjects in the supportive-care-only population with COVID-19-related hospitalization or who died due to any cause death through Day 29 and Day 60
- 4. Proportion of subjects in the supportive-care-only population who died due to any cause through Day 29 and Day 60
- 5. Proportion of subjects in the supportive-care-only population with COVID-19-related complications (e.g., death, hospitalization, radiologically confirmed pneumonia, acute respiratory failure, sepsis, coagulopathy, pericarditis/myocarditis, cardiac failure) through Day 29 and Day 60
- 6. Proportion of subjects in the supportive-care-only population with COVID-19-related medically attended visits (hospitalization, ER visit, urgent care or physician's office visit or telemedicine visit) or who died due to any cause through Day 29 and Day 60.
- 7. Proportion of subjects in the supportive-care-only population with COVID-19-related medically attended visits through Day 29 and Day 60
- 8. Proportion of subjects in the supportive-care-only population with COVID-19 symptom relapse through Day 29
- 9. Proportion of subjects in the supportive-care-only population with viral load rebound through Day 29
- 10. Proportion of subjects in the combination-antiviral population with COVID-19 symptom relapse through Day 29
- 11. Proportion of subjects in the combination-antiviral population with viral load rebound through Day 29

Version 5 June 24, 2024

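### Protocol 5.6 plans no Day 60 contact for subjects who leave the study, although six of the seven gated Day 60 tests need their hospitalization, visit or complication data after Day 29

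*Protocol*

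**What the plan says.** **Stopping drug versus leaving the study.** Protocol 5.6 separates the two. For the first group, "Subjects who prematurely discontinue study drug treatment should be encouraged to remain in the study and maintain the same protocol schedule". Table 1 includes Day 60, so they are covered. For the second group, those who "discontinue the study [prior to Day 29 (primary study period)] and are unable to maintain the same protocol schedule should complete early termination (ET) assessments" are also subject to a retrieval rule: "all attempts should be made to contact the subject at Day 29 (telephone contact is acceptable) to confirm key study endpoints, including hospitalization", with survival asked about as well. The section then closes with a general definition: "The end of the study for any individual subject will be defined as the 60-day follow-up contact". It contains no instruction to contact leavers at Day 60 and no rule for those who leave after Day 29.

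**Other measures against missing outcomes.** Protocol 8.3.1 and SAP 8.6.1 list two. One is a review of eCRFs for signs of unreported hospitalizations. The other is that "study staff may use a public information source to obtain information about survival status if a patient withdraws from the study".

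**What the SAP tests.** In SAP 8.5 the first test after the primary is "Proportion of subjects in the supportive-care-only population with all-cause hospitalization or all-cause death through Day 60". Items 2 to 7 are each tested at Day 29 and then at Day 60.

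**How withdrawal is handled.** SAP Table 2 assigns a treatment-policy strategy to the estimands built on hospitalization, visits, complications and death. For withdrawal or loss to follow-up it states: "The outcome measure up to point of study withdrawal will be used". SAP 6.8.1 imputes no missing efficacy data unless an endpoint's own section says so.

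**The concern.** The retrieval rule fits the protocol's primary endpoint, which ends at Day 29. The protocol's own Day 60 endpoints (section 8.2) are narrower: death, and COVID-19-related visit or death. The SAP adds Day 60 versions of all-cause hospitalization or death, COVID-19-related hospitalization or death, complications and others, and puts an all-cause Day 60 composite first in the gate. The collection rule for leavers does not extend to match.

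A treatment-policy estimand through Day 60 needs outcomes through Day 60 from everyone who can still be reached. Leavers may differ from those retained, and if leaving differs by arm, the uncollected events can shift the comparison. Because SAP 8.5 tests in sequence, a problem with the first secondary also bears on what follows it.

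**Working it through.** **1. Reproducing the plan's own figure.** The inputs come from SAP 4.3.1 and 11.2: placebo 4%, BEM 1.6%, one-sided 0.025, 90% power, 1:1 allocation.

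n per arm = [z(0.975)·√(2p̄q̄) + z(0.90)·√(p₁q₁+p₂q₂)]² / (p₁−p₂)², with p̄ = 0.028

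= [1.960·√0.054432 + 1.2816·√0.054144]² / 0.024² = 990.9, so 991 per arm and 1982 in total, as stated.

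1982 × 1.055 = 2091 (stated 2100), and 2100/0.95 = 2210.5 (stated 2210). These figures all belong to the Day 29 endpoint. The plan states no figure for Day 60 follow-up, and nothing here changes the sample size.

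**2. Counting the gated tests (SAP 8.5, after the primary).**

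| Items | Day 29 tests | Day 60 tests |
|---|---|---|
| 1 | 0 | 1 |
| 2-7 | 6 | 6 |
| 8-11 | 4 | 0 |
| Total | 10 | 7 |

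So 7 of 17 are Day 60 tests. Item 4 is death alone, which leaves 6 that use hospitalization, visit or complication data.

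**3. Looking for any route to leavers' outcomes over Days 30-60.**

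| Provision | Reaches leavers after Day 29? |
|---|---|
| Contact in protocol 5.6 | No: Day 29 only, and only for those leaving before Day 29 |
| Day 60 contact and SAE recording to Day 60 (protocol 3.1, Table 1, 7.2) | General provisions, not extended to leavers |
| eCRF review (protocol 8.3.1, SAP 8.6.1) | No: works on data already collected |
| Public-source lookup (same sections) | Survival only and optional, but with no Day 29 limit |
| Follow-up of unresolved AEs and SAEs (protocol 7.2, 7.3) | Only for events already open; does not ask about new hospitalizations or visits |

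The completer set (SAP 6.5.6) is defined by Day 29, and every analysis in SAP Table 4 runs through Day 29. No supplemental analysis there examines missing data at Day 60.

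**4. Size, under assumed rates.** The documents give neither a withdrawal rate nor an event rate for Days 30-60. Assume 3-8% leave without retrieval and 0.5-2% have a late event.

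Events missed = 2100 × share leaving × late-event rate

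- Low: 2100 × 0.03 × 0.005 = 0.3
- High: 2100 × 0.08 × 0.02 = 3.4

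If leaving differs by arm, say 5% in one and 10% in the other, the risk difference shifts by (0.10 − 0.05) × 0.5% to 2%, that is 0.025 to 0.10 percentage points. The shift favors whichever arm loses more subjects.

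**5. Whether that could change a test.** One-sided pooled chi-square, unstratified, 1050 per arm, BEM v placebo events:

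| Events | p |
|---|---|
| 17 v 42 (planning rates: 1050 × 0.016 = 16.8; 1050 × 0.04 = 42) | 0.0005 |
| 21 v 42 (four events added, all to BEM) | 0.0036 |
| 26 v 42 | 0.0243 |
| 27 v 42 | 0.0332 |

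At the planning rates, four extra BEM events, more than the upper figure in step 4, leave the conclusion unchanged. At 26 v 42, a single event moves the result across 0.025. The last two rows were chosen to sit at the boundary and are not a forecast.

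**The case against.** **Not all seven tests are affected alike.** A reader might infer that all seven Day 60 tests lack the data they need. The documents do not support that. The death test needs no hospitalization or visit data. It has a survival route that is optional but not limited to Day 29, and that route can also recover some deaths in the composites. The count is six. This objection stands.

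**Leavers are not entirely out of contact.** Unresolved AEs and SAEs are followed after the last visit or after participation ends, and the end of study is defined by the Day 60 contact. So it would be too strong to say that no information is sought from any leaver. But those rules follow existing events or define when the study ends. They do not collect new hospitalizations or visits and do not replace a Day 60 contact.

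**The denominator is not written down.** A reader might take it as stated that a leaver with no earlier event counts as event-free to Day 60. That is the likelier reading of Table 2 with the no-imputation rule, but neither document says it. This objection stands.

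**The effect is small and only partly recoverable.** Any result near the threshold is sensitive to one event, and at the planning rates nothing changes. Reasons for leaving include withdrawn consent and loss to follow-up (protocol 5.6), so many leavers cannot be, or may not be, called. SAP 4.3 and 5.1 say the final sample size had already been reached, so a new contact may help few subjects. This lowers the priority but does not remove the gap.

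**Conclusion.** The gap is real and narrow. As written, no provision plans to collect hospitalizations, visits or complications from study leavers over Days 30-60. Six of the seven gated Day 60 tests depend on such data, including the first secondary. Subjects who leave between Day 29 and Day 60 fall outside the retrieval rule altogether. The Day 60 death test rests, for leavers, on an optional lookup.

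The size depends on assumed rates because the documents supply none. The range of 0.3 to 3.4 missed events is an upper limit on what a contact could recover under those assumptions. It matters only if a Day 60 test is close, and the direction is unknown. A reader might infer that the main result or the power is at risk. Neither is: the primary ends at Day 29, where the retrieval contact exists, and the sample size was set for that endpoint. Priority: minor.

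**What to change.** **Protocol 5.6.** Require the contact attempt at Day 29 and again at Day 60 for subjects who leave before Day 29, and at Day 60 for those who leave between Day 29 and Day 60. Each contact should ask about hospitalization, COVID-19-related medically attended visits and survival, unless the subject refuses further contact.

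**SAP 8.6.1 and 8.7.** List the Day 60 contact, and a public-record survival check through Day 60, among the measures that reduce missing data for the Day 60 endpoints.

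**Cost.** One further telephone attempt per leaver, using a contact that other subjects already have, plus short SAP text. Changing 5.6 is a protocol amendment needing IRB/IEC approval (protocol 11.1). For subjects already past Day 60 the contact could only be retrospective, so recovery would be partial.
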